**Effects of High-Intensity Interval Training and Strength Training
On Levels of Testosterone and Physical Activity among Women
with Polycystic Ovary Syndrome.**

ClinicalTrials registration no: NCT04942366

Date: 9-March-2021

Study Protocol:

Informed consent had been taken from the participants before inclusion in the study. Baseline assessment was done before the start of the session. Both groups performed the warm up and cool down session. Group A performed High intensity interval training and Group B performed strength training exercises. The total length of this planned study was 36 sessions in 12 weeks i.e. three sessions per week. For baseline assessment, Laboratory test for total serum testosterone was performed, skinfold measurement for body fat had been taken by the chief examiner and International physical activity questionnaire for physical activity measurement was filled by the subjects. At the end of the last intervention session, all outcome measures were reassessed (post- intervention). All the activities were supervised by a physical therapist.

Warm Up:

A total of 10 minute warm up of light to moderate intensity cardiorespiratory activity for HIIT group A and muscular endurance activity for ST group B.

High Intensity Interval Training:

High intensity interval training for group A was performed thrice a week using a treadmill. The protocol of each session that was followed is four sets of 4 minute interval session (at 90%-95% of the individual HR max calculated by using the karvonen method) and each set had been followed by 3 minute of moderate intensity exercise (at 70% of individual HR max, calculated through karvonen method). Each session was of 45 minutes duration including warm up and cool down period. To ensure that the correct exercise intensity is

performed; subjects wore heart rate monitors during training sessions.

Strength Training:

Strength training for group B was performed thrice a week, each session comprised of 8 dynamic drills (with resistance of 60 – 70 % of 1 repetition maximum). Eight exercises on the major muscle groups were included in this session (Squats, deadlift, lunge, standing bent rowing, shoulder press, bench press, push-ups, and abdominal crunches). Each drill consisted of 10-12 repetitions x 3 sets. Each set was separated by one minute rest. Equipment like dumbbells had been provided. Each individual was assessed and according to that progression of strength training had been considered, weight (kg) was increased according to 1RM method that had been assessed after every week. 1RM method is the gold standard for dynamic strength assessment, it is the maximum weight that can be moved in one repetition. 1RM is determined through four trials that starts with gradually increasing resistance of 2.5kg-20kg until the subject is unable to complete repetitions. The final weight achieved is selected as absolute 1-RM. Total exercise time for this session was 45 minutes, warm up and cool down period included.

Cool Down:

A total of 10 minute cool down of light to moderate intensity cardiorespiratory activity for HIIT group A and muscular endurance activity for ST group B.

Exercise termination criteria:

Exercise based intervention were prematurely terminated when anyone of the following occurred as per the American College of Sports Medicine Criteria (2013),

- Modified Borg dyspnea scale is at level 8 or higher.
- Decrease in oxygen saturation at less than 90%.
- On the request of the patient.

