**Effects of High-Intensity Interval Training and Strength Training
On Levels of Testosterone and Physical Activity among Women with
Polycystic Ovary Syndrome.**

ClinicalTrials registration no: NCT04942366

Date: 9-March-2021

Statistical Analytical Plan:

For the analysis, the data was entered and analyzed in MedCalc software version 19.0.5.

Descriptive statistics were performed for demographic information and this data is presented in terms of frequency and percentage. Shapiro-Wilk test was used to determine the normality of data.

For BMI: Shapiro-Wilk test was used to determine the normality of data and the data was normally distributed so paired T-test was performed for within group analysis. Independent T-test was performed for the comparison between the two groups.

For Serum testosterone: Shapiro-Wilk test was used to determine the normality of data and the data was normally distributed so paired T-test was performed for within group analysis. Independent T-test was performed for the comparison between the two groups.

For Body fat percentage: Shapiro-Wilk test was used to determine the normality of data. The data was not normally distributed so, Wilcoxon sign rank test was performed for within group analysis. Independent T-test was performed for the comparison between the two groups.

For IPAQ: Shapiro-Wilk test was used to determine the normality of data. The data was not normally distributed so, Wilcoxon sign rank test was performed for within group analysis. Independent T-test was performed for the comparison between the two groups.

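### Assignment to Group A or B is not described, and the groups are compared without baseline adjustment, so a baseline difference between them can pass for a difference between programmes

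*Protocol*

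**What the plan says.** The protocol's opening account, under the heading Study Protocol, gives the order of events. Before training it places two steps: "Informed consent had been taken from the participants before inclusion in the study. Baseline assessment was done before the start of the session". The next statement about groups is that "Group A performed High intensity interval training and Group B performed strength training exercises". Neither document mentions randomisation, a sequence, concealment, an allocation ratio, matching or any other rule for forming the groups.

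The SAP, under Statistical Analytical Plan, repeats one sentence for each of BMI, serum testosterone, body fat percentage and IPAQ: "Independent T-test was performed for the comparison between the two groups". It names no covariate or stratification, and does not say whether the test uses post-intervention values or changes from baseline. Baseline values enter the stated tests only within groups; for testosterone and BMI, for example, "the data was normally distributed so paired T-test was performed for within group analysis". Demographic data are descriptive only: "Descriptive statistics were performed for demographic information and this data is presented in terms of frequency and percentage".

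Both documents carry a title beginning "Effects of High-Intensity Interval Training and Strength Training".

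**The concern.** An unadjusted t-test between two groups estimates the difference between programmes when assignment is unrelated to prognosis. Nothing in the documents secures that condition. Two teams could follow this protocol to the letter, one with a concealed random list and the other letting women choose, and both would run the same t-test. Only the first would have grounds for a causal statement.

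The comparison is also exposed if assignment was random. In small arms a chance gap at baseline carries into the post-intervention values, and the plan leaves it there although the baseline measurements exist. What is at stake is the only between-group evidence on all four outcomes. Physical activity is one of them: the women complete that questionnaire themselves, and it could plausibly be related to the choice of programme if choice played a part.

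**Working it through.** **What the documents supply.** There is no sample size, variance, significance level or allocation ratio, so there is no stated figure to reproduce. Baselines do exist. The protocol records testosterone ("For baseline assessment, Laboratory test for total serum testosterone was performed"), skinfold body fat and IPAQ before training. BMI is not in that list, but a paired BMI test in the SAP requires a baseline BMI.

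**Assumptions for an illustration.** n = 20 to 40 per arm; no true difference between programmes; a systematic baseline gap d = 0.3 to 0.5 SD from selection; pre-post correlation r = 0.5 to 0.7; equal SDs of 1 before and after; two-sided 5% test.

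**Case 1: the gap regresses towards a common mean.**
- Post values: shift = r·d, SD = 1, non-centrality = r·d·√(n/2).
- Changes: shift = (1−r)·d, SD = √(2(1−r)), non-centrality = (1−r)·d/√(2(1−r))·√(n/2).
- The rejection rate comes from the non-central t distribution with 2n−2 degrees of freedom.

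| Test on | n | d | r | Shift (SD) | Non-centrality | False-positive rate |
|---|---|---|---|---|---|---|
| Post, lowest | 20 | 0.3 | 0.5 | 0.15 | 0.15 × √10 = 0.47 | 7.5% |
| Post, highest | 40 | 0.5 | 0.7 | 0.35 | 0.35 × √20 = 1.57 | 34.0% |
| Change, lowest | 20 | 0.3 | 0.7 | 0.09 | (0.09/0.775) × √10 = 0.37 | 6.5% |
| Change, highest | 40 | 0.5 | 0.5 | 0.25 | (0.25/1) × √20 = 1.12 | 19.7% |

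With d = 0 the rate is 5%.

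**Case 2: the gap is a stable trait and carries over in full.** The shift on post values is d. For n = 20, d = 0.3 the non-centrality is 0.3 × √10 = 0.95 and the rate is 15%. For n = 40, d = 0.5 it is 0.5 × √20 = 2.24 and the rate is 60%. The shift on changes is zero, so that test keeps 5%.

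**Chance gaps under random assignment.** The standard error of a baseline mean difference is √(2/n) SD: √(2/20) = 0.32 and √(2/40) = 0.22. A gap of 0.3 SD is therefore unremarkable in arms of this size. Over repeated randomisations the t-test still has its 5% rate. In the one trial that was run, though, a realised gap d moves the expected post-value difference by r·d, which is 0.15 to 0.35 SD for the gaps above.

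**What baseline adjustment does.** In Case 1, and for a chance gap under randomisation, regressing the post value on group and baseline removes the shift. It also reduces the residual variance to 1−r² of the post-value variance: 0.75 at r = 0.5 and 0.51 at r = 0.7. In Case 2 it leaves d − r·d = (1−r)·d, or 0.09 to 0.25 SD. Adjustment is therefore a gain under randomisation, but it does not substitute for it.

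**The case against.** A reader might infer that the trial was not randomised, or that women were sorted by preference, fitness or therapist choice. The documents do not support that. They are silent, and no such mechanism is mentioned. The text is short throughout and also omits eligibility and sample size, so an unreported random allocation is quite possible. If allocation was random and concealed, the bias is zero in expectation and the missing description is only a reporting gap.

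A reader might also say that the SAP interprets its t-test as a causal effect of exercise type. No sentence in it does so. That reading comes from the title combined with the fact that this is the only between-group test. It is a fair inference, not a stated claim.

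The numbers are open to challenge as well. Every input is assumed, and Case 1 depends on regression to a common mean. Case 2 moves the rates in both directions: down to 5% on changes and up to 60% on post values. The ranges therefore do not bound the problem and measure nothing about this trial.

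All of these objections stand as limits. Two facts remain: the assignment method is not stated, and baseline values already collected are left out of the between-group comparison.

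**Conclusion.** The point holds as a gap in the documents joined to an avoidable weakness in the analysis. How women were placed in the two groups is not stated. For all four outcomes the between-group comparison takes no account of baseline through adjustment, so a baseline difference of either origin can look like a difference between programmes.

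The size for this trial is unknown. Under the assumptions shown, a systematic gap of 0.3 to 0.5 SD raises the nominal 5% to between 7.5% and 34% on post values and between 6.5% and 20% on changes if the gap regresses, or to 15% to 60% on post values and no inflation on changes if it is stable. Those figures describe selection. Under true randomisation the 5% rate holds over repeated trials, and the loss is in precision and in exposure to a chance gap. A conclusion that the trial was non-randomised, or that its result is biased, would go beyond the documents.

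**What to change.** **SAP.** Replace each between-group t-test with a linear model of the post-intervention value on group and the baseline value of the same outcome. Use a rank-based or robust version for body fat percentage and IPAQ, which the SAP calls non-normal. Report the adjusted difference with its confidence interval. This also settles whether post values or changes are compared. Other covariates should be added only if they can be shown to have been recorded at baseline; age, for example, is not named in either document.

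**Protocol.** State how women were actually assigned, when this happened relative to consent and baseline assessment, and whether the next assignment was concealed. Both documents are written in the past tense, so the task is to record what was done. Specifying a new allocation procedure now would be moot.

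**If no random, concealed sequence can be documented.** Call the groups non-randomised, keep the adjusted model, limit the conclusion to an association between programme and outcome, and say that adjustment does not remove unmeasured selection.

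**Cost.** One regression per outcome on data the trial already collects, a paragraph in the protocol and, in the last case, a weaker claim. No new measurements are needed.

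### The only post-baseline assessment is tied to the last training session rather than a fixed date, so a woman who stops early has either no week-12 value or one taken at an unequal time

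*Protocol*

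**What the plan says.** The Study Protocol section gives two measurement points. For the first: "Baseline assessment was done before the start of the session". For the second: "At the end of the last intervention session, all outcome measures were reassessed". The programme length is also given: "The total length of this planned study was 36 sessions in 12 weeks i.e. three sessions per week". No interim outcome visit is described, and no outcome visit is set by time since baseline.

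Under Exercise termination criteria the Protocol foresees early stopping: "Exercise based intervention were prematurely terminated when anyone of the following occurred". Two of the triggers are acute signs (a dyspnoea score and an oxygen saturation limit). The third is "On the request of the patient". The text does not say whether a trigger ends one session or the whole programme, or what happens to outcome collection afterwards.

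The SAP, under Statistical Analytical Plan, uses paired tests within groups. For BMI and serum testosterone, "paired T-test was performed for within group analysis"; for body fat percentage and IPAQ it is the Wilcoxon signed-rank test. All four outcomes are compared between groups by an independent t-test, without saying whether on post values or on changes. The SAP names no analysis population and no missing-data method.

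**The concern.** When the outcome visit hangs on attendance, stopping training also disrupts measurement. Stopping a demanding exercise programme may well relate to tolerance and response. The two programmes ask for different kinds of effort: treadmill intervals at 90–95% of maximum heart rate in one arm, resistance at 60–70% of one-repetition maximum in the other. Unequal stopping is therefore plausible, though not documented.

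If poor responders stop more often and are not measured, the change within each arm looks better than it was for all women who started. The arm that loses more women then gains an undeserved advantage in the comparison. If women who stop are measured when they leave, the tests mix different lengths of training and follow-up under one label. In either case a reader cannot tell whose data the results describe.

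**Working it through.** **Figures in the plan.** No sample size, SD, dropout rate or power is stated, so there is no design figure to reproduce. The one piece of arithmetic is consistent: 12 weeks × 3 sessions = 36 sessions.

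**Two readings of the last session.**
- *Session 36.* A woman who stops never reaches it and has no scheduled post value. The paired t and Wilcoxon tests need both values, so she is lost within her group. The independent t-test needs a post value whether it is run on post values or changes, so she is lost there too. It is the missing value, not the pairing, that removes her from the between-group comparison.
- *Her own last session.* A post value may exist, but at some point before week 12. The problem is then unequal timing, not missing data.

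**Illustrative size under the first reading.** All inputs are assumptions: dropout share d of 10%, 20% or 30%, and correlation r of 0.3 to 0.5 between change and a latent score whose lowest fraction d stops. The bias in the mean change among those measured, in SD of change and in the direction of benefit, is

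r × φ(z_d) / (1 − d),

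where φ is the standard normal density and z_d the normal quantile at d.

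| d | φ(z_d)/(1 − d) | within-arm bias, r = 0.3 | r = 0.5 |
|---|---|---|---|
| 10% | 0.195 | 0.06 | 0.10 |
| 20% | 0.350 | 0.11 | 0.18 |
| 30% | 0.497 | 0.15 | 0.25 |

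Between-arm bias with no true difference is r × the difference in multipliers:
- 20% vs 10%: (0.350 − 0.195) × r = 0.155r, or 0.047 to 0.078 SD.
- 30% vs 10%: (0.497 − 0.195) × r = 0.302r, or 0.091 to 0.151 SD.
- Equal dropout and the same r in both arms: 0.

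**Cross-check by a simpler model.** If those who stop differ from completers by a gap g in mean change, the within-arm shift is g × d and the between-arm shift is g × (d_A − d_B). For g of 0.25 to 1.0 SD, 20% dropout shifts an arm's change by 0.05 to 0.20 SD, and 30% vs 10% shifts the comparison by 0.05 to 0.20 SD. The two models overlap.

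**Precision.** Losing a share d widens the standard error by 1/√(1 − d): 1.054, 1.118 and 1.195, or about 5%, 12% and 20% for 10%, 20% and 30%.

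**The case against.** The strongest reply is that the Protocol simply gives the normal timing of an end-of-treatment visit, and that everything beyond this is inferred from silence. Much of that stands. A reader might infer that women who stopped have no usable post value and that the trial is a completers-only comparison. The documents do not support this: they do not say that anyone stopped, that anyone who stopped went unmeasured, or that only completers were analysed. On the second reading of the last session a post value could exist.

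The termination criteria are also weak evidence of withdrawal. They may concern a single exercise session, after which the woman returns. The concern does not need them, however, since a woman can stop attending for any reason.

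The sizes rest wholly on assumption. The between-arm figures need unequal dropout. If one assumes 20 to 50 women per arm, the standard error of an arm difference is √(2/20) = 0.32 to √(2/50) = 0.20 SD, larger than any between-arm bias in the 0.05 to 0.15 SD range. One could also claim that within-arm change is inflated by 1/(1 − d), that is 1.11 to 1.43 for 10% to 30% dropout. That requires women who stopped not to have changed at all, although they would have had some training.

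What the reply does not remove is the structural weakness. As written, neither reading gives a woman who stops a scheduled week-12 value, and no rule says how she is analysed. A standard error larger than the bias does not make the bias harmless, because bias does not average out.

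**Conclusion.** The point holds as a weakness of design, not as a demonstrated bias. The sole post-baseline assessment follows attendance instead of the calendar, so early stopping leads to a missing value or to one at an unequal time.

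The size cannot be known from the documents. It is nil if every woman completed. Between arms it is nil if dropout and selection are equal, although a within-arm bias would remain. Under the assumed dropout of 20% or 30% against 10%, with r of 0.3 to 0.5, the between-arm bias is about 0.05 to 0.15 SD. These figures show what is possible; they are not an estimate for this trial. The change is worth making because it is cheap and because the numbers per arm would show at once whether the problem arose.

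**What to change.** **If assessments can still be scheduled.** Set the post-assessment at 12 weeks after baseline for every woman allocated, whatever her attendance. Compare the groups as allocated on the week-12 value adjusted for baseline (ANCOVA), in place of the independent t-test. Keep the completers analysis as a sensitivity analysis. State whether the termination criteria refer to a session or to the programme.

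**If data collection is finished**, as the past tense of both documents suggests, a recall visit may no longer be possible. Three steps remain:
- Report the numbers allocated, stopped and measured per arm, and the time of the post value for any woman who stopped.
- Run the baseline-adjusted comparison by allocated group on all women with a post value. This does not by itself remove bias if stopping depended on response.
- Add a sensitivity analysis in which missing women in each arm are given a range of mean changes δ, so that the arm mean is (1 − d) × observed mean + d × δ. No change is one case. It should not be the only one, since filling in a single value also understates uncertainty.

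**Cost.** Wording in both documents, plus one follow-up assessment (blood test, skinfolds, questionnaire) for women who stop. The effect estimate may be somewhat smaller, because it then describes all allocated women. The retrospective version needs no new data.

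### Do the mixed heart-rate wording and the 48-against-45-minute sum for the HIIT sessions call for a change to the plan?

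*Protocol*

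**What the plan says.** The Protocol section High Intensity Interval Training sets the work intervals "at 90%-95% of the individual HR max calculated by using the karvonen method" and the recovery periods "at 70% of individual HR max, calculated through karvonen method". It gives no formula, no resting heart rate and no source for the maximum. It adds that "subjects wore heart rate monitors during training sessions" so that intensity could be kept correct.

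For timing, the same section says "The protocol of each session that was followed is four sets of 4 minute interval session" and that "each set had been followed by 3 minute of moderate intensity exercise". The Warm Up section has "A total of 10 minute warm up of light to moderate intensity cardiorespiratory activity for HIIT group A", and the Cool Down section has "A total of 10 minute cool down of light to moderate intensity cardiorespiratory activity for HIIT group A". The stated total is "Each session was of 45 minutes duration including warm up and cool down period". The Strength Training section gives the same total of 45 minutes for the other arm.

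The SAP lists paired and independent t-tests and the Wilcoxon signed-rank test for BMI, serum testosterone, body fat percentage and the IPAQ.

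**The concern.** Two things look wrong.

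- **Scale.** A percentage of maximum heart rate is p × HRmax. The Karvonen method, on its usual definition, adds p × (HRmax − resting rate) to the resting rate. If the label and the method name are both taken literally, one stated percentage gives two targets, and a monitor can confirm correct intensity only against one.
- **Time.** The listed parts do not add to the stated session length.

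At stake is whether another team could reproduce the HIIT arm: how hard the recovery periods were, how far intensity fell between work and recovery, and whether there were three or four recoveries. Since 45 minutes is the nominal length in both arms, a longer HIIT session would also mean that the arms were not matched on time.

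**Working it through.** **Session time (inputs all from the Protocol).** Warm-up 10 min, four work sets of 4 min, recovery of 3 min, cool-down 10 min.

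- A recovery after all four sets: 10 + 4 × 4 + 4 × 3 + 10 = 10 + 16 + 12 + 10 = 48 min.
- Three recoveries, one between each pair of sets: 10 + 16 + 9 + 10 = 45 min, which reproduces the stated figure. The total is also 45 if the fourth recovery is counted inside the cool-down.
- Difference: 3 min per session, or 3/45 = 6.7%. Over the planned 36 sessions this is 36 × 3 = 108 min against 36 × 45 = 1,620 min.
- Recovery as a share of the core: 12 of 28 min (43%) with four, 9 of 25 min (36%) with three.

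**Heart-rate scale.** The documents give no heart rates and no formula. I assume the usual Karvonen definition, HRmax of 180 to 200 and a resting rate of 60 to 80 beats per minute (bpm).

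- Target on the maximum scale: p × HRmax.
- Target on the reserve scale: rest + p × (HRmax − rest).
- Gap: (1 − p) × rest, which does not depend on HRmax.

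| Target | Gap, rest 60–80 | Maximum scale, HRmax 190 | Reserve scale, HRmax 190, rest 70 |
|---|---|---|---|
| Recovery, 70% | 18–24 bpm | 133 | 154 |
| Work, 90% | 6–8 bpm | 171 | 178 |
| Work, 95% | 3–4 bpm | 180.5 | 184 |

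If the resting rate were as high as 90, the gaps would be 27, 9 and 4.5 bpm.

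- Overlap of the two work bands: 0.95 × HRmax − (0.90 × HRmax + 0.10 × rest) = 0.05 × HRmax − 0.10 × rest. This is 1 bpm at 180/80, 2.5 at 190/70 and 4 at 200/60.
- Drop from the lower work limit to recovery: 0.20 × HRmax = 36–40 bpm on the maximum scale; 0.20 × (HRmax − rest) = 20–28 bpm on the reserve scale. At 190/70 these are 38 and 24 bpm.

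The ambiguity therefore lies mainly in the recovery target; the work bands nearly coincide.

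**Reach into the analysis.** All four SAP outcomes are compared within and between the two groups. None is defined by achieved heart rate or minutes trained. The SAP names no covariate, analysis set or adherence rule that uses either. Choosing one heart-rate reading or one recovery count changes no input to any listed test.

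**The case for a change.** The strongest case for acting is that the work-to-recovery contrast defines an interval programme, and in the worked example it shrinks from 38 to 24 bpm, by more than a third, depending on the reading. This is one of only two arms. Supervision and monitors protect fidelity only if the target is unique, and the text does not say which target was used. Stating the scale, the formula, the source of the maximum and the number of recoveries would cost only a few words.

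Most of this stands as a comment on the description. The written Protocol alone does not let a reader derive a target in bpm or tell three recoveries from four, and those statements must be reconciled wherever the intervention is reported.

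It does not show that staff lacked a target. The sentence can be read as a percentage of a maximum obtained by the named method, or as loose labelling for reserve; under either, each participant has a single target. All activities were supervised by a physical therapist. The bpm figures measure the distance between two interpretations under assumed heart rates, not an error known to have occurred. On time, the stated 45 is met exactly by a simple reading, so unequal session length between the arms is not demonstrated.

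**Conclusion.** The observation is accurate but minor, and no change to the plan follows. It combines a gap in description (which heart-rate scale) with what may be a clerical slip (whether a separate recovery follows the last set). The recovery target is uncertain by 18 to 24 bpm and the work targets by 3 to 8 bpm, given the usual Karvonen definition and a resting rate of 60 to 80; the session length is uncertain by 3 minutes in 45. The time figures need no assumption.

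The sessions are described as already delivered, so clearer text would record what was done and could not change what participants received. It would not alter any outcome or test in the SAP. I take no position on which intensity or schedule applied. The trial team can settle both points from its own knowledge of the sessions when it describes the intervention.
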